Part E: MOR03087 (weekly/biweekly treatment) in combination with LEN+DEX

- Dose level 7e: 8.0 mg/kg
- Dose level 8e: 16.0 mg/kg

Each 28-day cycle will consist of:

MOR03087 infusion on Days 1, 8, 15, and 22 of the cycle. In Cycle 1, a loading dose will additionally be administered on Day 4 of the cycle.

Only for dose level 8e, for cycle 4 and onwards each 28-day cycle will consist of: MOR03087 infusion on Day 1 and 15 of the cycle.

Subjects who have received treatment beyond Cycle 3 will be switched to the biweekly schedule at the next Day 1 or Day 15 visit. In exceptional cases, and after discussion between the investigator and the sponsor, the treating physician may determine that it is in the best interest of the subject to remain on the weekly MOR03087 schedule, in which case the sponsor should be informed accordingly.

Oral LEN 25 mg on Days 1-21 of the 28-day cycle.

Oral DEX 40 mg (\leq 75 years old) or 20 mg ($>$ 75 years old) on Days 1, 8, 15, and 22 of the

28-day cycle.

For subjects in Cohort 8e who switch to biweekly MOR03087 treatment from Cycle 4 onwards, the DEX treatment schedule will remain unchanged (Day 1, 8, 15 and 22).

In Cycle 1 DEX is to be added to the loading dose on Day 4.

Following completion of Parts D and E (dose escalation of MOR03087 in combination with POM + DEX and LEN + DEX), the MTD and/or recommended dose in each part will be confirmed in a minimum of 6 subjects.

All cohorts:

Based on the individual risk/benefit ratio, subjects who have an ongoing response of at least stable disease (SD) may continue treatment with the assigned study regimen until disease progression or until a maximum of 3 years after first treatment. In case subjects present with progressive disease or with no better status than SD after 4 treatment cycles starting with Cycle 1 Day 1, the investigator may add a low weekly dose of DEX to the regimen at his/her discretion, provided DEX is not already part of the treatment regimen.

After study drug discontinuation due to reason other than disease progression and other than withdrawal of consent, all subjects will return for a follow-up visit 1 and follow-up visit 2. Further follow-up visits will be conducted at 4-week intervals until the subject is progressive, begins subsequent anti-myeloma therapy, or dies.

All subjects will be followed up for a maximum of 3 years after first administration of study drug.

Dose Escalation Process:

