For all scales (categories), the Raw Score (RS) is the mean of the component items.

In case of missing items within an answered questionnaire, the RS for the scale will only be calculated if at least half of the items from the scale have been answered. In this case the mean will be calculated only including those questions which have been answered.

The RS will be transformed into a standardized score using a linear transformation so that scores range from 0 to 100; a higher standardized score represents a higher ("better") level of functioning for functional scales, or a higher ("worse") level of symptoms for symptom scales. The following formula will be used for transformation:

- Functional scales: $Score = [1 - (RS-1)/range] * 100$
- Symptom scales: $Score = (RS-1)/range * 100$

A global score based upon the sum of all items of the QLQ-C30 and/or the QLQ-MY20 will not be calculated according to the recommendations of the EORTC data center. The Global health status / QoL scale (based on questions 29 and 30) will be used as an overall summary measure for the QLQ-C30.

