7.3.6 Exposure

Table 5 shows the variables that will be calculated to measure exposure to study drugs (MOR03087, DEX, LEN, POM). Exposure to MOR03087 will be calculated for all subjects, exposure to LEN and POM will be only calculated for subjects in the respective combination therapy cohorts. Dexamethasone exposure will be derived for subjects in the dose-escalation part

receiving weekly MOR03087 treatment plus dexamethasone, and in subjects in both combination therapy cohorts. In cohorts where dexamethasone may be added later, dexamethasone intake will be summarized within the concomitant medication table.

Table 5 Derived Variables for Exposure

Exposure to Any Study Drug		
Variables calculated on a per-subject basis	Duration of treatment [months]	(date of last dosing day of any IMP – date of first dosing day of any IMP + 1)/██████████
Exposure to MOR03087		
Variables calculated for each study drug administration	Percentage of actual volume administered vs. planned volume [%]	
Actual volume administered [mL]/planned volume [mL]*100%
 
Note: The planned volume is either 100 mL or 250 mL.
 
In case no actual volume administered is given, the value will be set
 
 • to the planned volume in case dosing modified is answered with “No” • to 0 in case dosing modified is answered with “Yes” and the type of modification is “Infusion not given” • to 0 in case infusion page is not filled out, but visit took place, and infusion planned according to treatment schedule and visit date is before last date of dosing • to missing in case dosing modified is answered with “Yes” and type of modification is other than “Infusion not given”. 
In case actual volume is 0 and planned volume is unknown, the percentage will still be calculated as 0%.

	Actual dose administered [mg/kg]	
(Actual volume administered [mL]/planned volume [mL])*Assigned dose [mg/kg]
 
Note: This calculation assumes that the study drug solution is prepared correctly and contains the correct amount of study drug.

	Actual dose administered [mg]	
(Actual volume administered [mL]/planned volume [mL])*Assigned dose [mg/kg]* Weight[kg]
 
Note: Weight will be taken from the same visit from the Vital Signs form. In case no weight is available for this visit the most recent previous available weight will be

		taken.
	Duration of infusion [min]	Duration, calculated as stop time of infusion – start time of infusion

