	Shortest infusion duration category per subject	Select from all available infusion duration categories per subject the shortest one in the order of <40min; >=40 min to <1h; >= 1h to <2h; >= 2h to <3h, and ≥3h
Exposure to Lenalidomide		
Variables calculated on a per-subject basis including data of all cycles	Number of days treated	Sum of durations of intake [=Start date – Stop date + 1] over all entries (in the eCRF LEN administration log) with non-zero dose
	Total actual dose taken [mg]	Sum of (durations of intake * dose [mg]) over all entries (in the eCRF LEN administration log)
	Average daily dose taken during days treated [mg/day]	Total actual dose taken [mg]/ Number of days treated
	Average daily dose taken during study [mg/day]	Total actual dose taken [mg]/ Duration of treatment [weeks] *7
	Percentage of actual dose vs. planned dose [%]	Total actual dose taken [mg]/ Planned dose [mg] Where planned dose = sum of (starting dose of each cycle * 21 days), calculated over all cycles initiated. Starting dose of each cycle is taken from eCRF LEN administration page for Day 1 of each cycle

	Number of days with missed doses	Sum of durations of intake of 0 dose [=Start date – Stop date + 1] over all entries (in the eCRF LEN administration log) with reason other than “Subject is in Rest Period between Day22 and Day28”
	Any dose reduction	Any reduced dose applications (compared to starting dose in first cycle)
	Any permanent discontinuation of LEN but continuation of MOR03087	Discontinuation of LEN but continuation of MOR03087 during at least 2 MOR03087 infusions until last MOR03087 dosing day
Exposure to Pomalidomide		
Variables calculated on a per-subject basis including data of all cycles	Number of days treated	Sum of durations of intake [=Start date – Stop date + 1] over all entries (in the eCRF POM administration log) with non-zero dose
	Total actual dose taken [mg]	Sum of (durations of intake * dose [mg]) over all entries (in the eCRF POM administration log)
	Average daily dose taken during days treated [mg/day]	Total actual dose taken [mg]/ Number of days treated
	Average daily dose taken during study [mg/day]	Total actual dose taken [mg]/ Duration of treatment [weeks] *7

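### The SAP formula for average daily LEN and POM dose during study lacks parentheses and, read left to right, gives 49 times the intended mg/day

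*SAP*

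**What the plan says.** SAP section 7.3.6, Table 5, lists the derived exposure variables. The LEN and POM blocks each contain a row named "Average daily dose taken during study [mg/day" (per-day unit), and both give the same derivation: "Total actual dose taken [mg]/ Duration of treatment [weeks] *7".

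The numerator for LEN is "Sum of (durations of intake * dose [mg]) over all entries (in the eCRF LEN administration log"; POM has the matching entry from its own log. The row just above averages over treated days only: "Total actual dose taken [mg]/ Number of days treated".

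Treatment duration is defined once, in the block of Table 5 on exposure to any study drug, under "Duration of treatment [months". It is the date of the last dosing day of any IMP minus the date of the first, plus one, divided by a constant that is redacted in the public copy. SAP section 10.7 says that all per-subject exposure variables will be summarized descriptively, with the LEN and POM summaries limited to the respective combination cohorts.

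**The concern.** The label asks for mg per day. Dividing total mg by weeks gives mg per week; multiplying that by 7 moves further from mg per day. A programmer who enters the expression as printed gets a number that is not a daily dose.

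The row has a purpose of its own, because it is the only LEN or POM measure in Table 5 that averages intake over calendar time. The average over treated days ignores holds. The percentage of planned dose is based on each cycle's own starting dose times 21 days, so it does not register a lower dose set at the start of a cycle, or a delay between cycles. SAP section 4.3 plans to re-run all analyses at follow-up, so an uncorrected formula would be applied twice.

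**Working it through.** The plan gives no numerical value for this variable, so there is no figure to reproduce. The check is one of units, followed by worked cases.

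**Inputs**
- LEN schedule, SAP section 3.1, Part E: "Oral LEN 25 mg on Days 1-21 of the 28-day cycle". Full dosing is 25 × 21 = 525 mg per cycle.
- POM schedule, SAP section 3.1, Part D: 4 mg on 21 days of each 28-day cycle. Full dosing is 4 × 21 = 84 mg per cycle.
- Formula: SAP section 7.3.6, Table 5, as quoted.
- Software: SAS (SAP section 7.1), which gives division and multiplication equal rank and evaluates them left to right.

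**General result.** Let D be total mg and W the duration in weeks, so that the duration in days is 7W.
- Intended mg/day: D / (7W).
- As written, left to right: (D / W) × 7.
- Ratio: 7 × 7 = 49, whatever D and W are.

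**Worked cases, full dosing**

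| Drug | Total mg | Duration (days) | As written | Intended (mg/day) |
|---|---|---|---|---|
| LEN | 525 | 28 | 525/4 × 7 = 918.75 | 525/28 = 18.75 |
| POM | 84 | 28 | 84/4 × 7 = 147 | 84/28 = 3.0 |
| LEN | 525 | 22 | 1169.32 | 525/22 = 23.86 |
| POM | 84 | 22 | 187.09 | 84/22 = 3.82 |
| LEN | 3150 (six cycles) | 168 | 918.75 | 3150/168 = 18.75 |
| POM | 504 (six cycles) | 168 | 147 | 504/168 = 3.0 |

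The 22-day rows matter because Table 5 counts duration to the last dosing day. A subject who stops after one cycle has a last infusion on Day 22, so the final rest days are not counted. The daily averages change; the ratio of 49 does not.

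**How the SAP reads the same notation elsewhere.** Two other expressions have the form a/b*c:
- Table 5, infusion volume: "Actual volume administered [mL]/planned volume [mL]*100" per cent. With 90 mL given of 100 mL planned, left to right gives 90; grouping the last two terms gives 90/(100 × 100) = 0.009.
- Section 7.3.5, symptom scales: "Score = (RS-1)/range * 100". With a raw score of 3 and a range of 3, left to right gives 66.7; grouping gives 2/300 = 0.0067.

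Both are correct only when read left to right. The LEN and POM rows are correct only when the last two terms are grouped: 525/(4 × 7) = 18.75 and 84/(4 × 7) = 3.0. No text in the SAP tells the reader to switch rules.

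**The case against.** The best defence is that the intention is obvious. The row is labelled per day, and weeks times 7 is days, so the author almost certainly meant that product as the denominator. On that reading the formula is right. This stands as an account of the cause, and a reader should not infer a mistaken method. It does not make the printed expression correct, because the grouping is stated nowhere and the SAP's own notation runs the other way.

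A second objection is that the literal reading is selective. The same table writes the length of an intake period as start date minus stop date plus one. Taken literally, a 21-day entry has length 1 − 21 + 1 = −19, LEN total dose becomes 25 × −19 = −475 mg, and the row gives −475/4 × 7 = −831.25. This is fair: the factor of 49 takes the numerator as intended. It does not rescue the denominator.

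Third, the consequences are small. About 919 mg/day of LEN, or 147 mg/day of POM, would be printed beside a correctly defined treated-day average of 25 mg or 4 mg under full dosing. Missed days, dose reductions, permanent discontinuation and percentage of planned dose are also tabulated. This stands, although none of those rows replaces the calendar-time average.

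A reader might also infer that the duration in weeks is undefined, or that the SAP leaves open whether LEN/POM dates or any-IMP dates apply. The documents do not support either. Table 5 gives the day count and ties it to any IMP; only the divisor for months is redacted, and weeks are that count divided by 7. Switching to LEN or POM dates would change the measure. In an assumed case with 1050 mg LEN over two cycles and MOR03087 continued through six, the average is 1050/168 = 6.25 mg/day on any-IMP dates and 1050/56 = 18.75 on LEN dates.

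**Conclusion.** The derivation is wrong as printed for both drugs, by a factor of exactly 49 when evaluated left to right. This assumes that the total-dose numerator is computed as intended. The likely cause is a missing pair of parentheses.

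The reach is narrow: one descriptive exposure row per drug, in Parts D and E only. It would be tempting to conclude that the trial's safety or dose conclusions are at risk, but the documents do not support that. Average daily dose is not among the endpoints in SAP section 2.2. The MTD in SAP section 10.1 rests on DLTs in the DLT Evaluable Population. The exposure-adjusted incidence rates in SAP section 10.2 use their own time-at-risk definition. Values this implausible would also be likely to be noticed on review. The point is still worth correcting, because this is an operative rule for a variable that section 10.7 requires to be tabulated, and a silent repair in the program would leave code and SAP in disagreement.

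**What to change.** In the LEN and the POM rows of Table 5, place the product in parentheses: total actual dose in mg / (treatment duration in weeks × 7). Equivalently, divide total actual dose by the duration in days that Table 5 already uses, from the first to the last dosing day of any IMP, inclusive. Keep the any-IMP dates, so that the correction does not alter what is measured.

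The reversed start and stop dates in the intake-duration entries are a separate slip and can be put right in the same edit.

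The cost is one line of SAP wording per drug. No data collection, sample size, endpoint or clinical rule changes.

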	Duration of infusion [categorized]	Duration will be categorized into: <40min; <1h, <2h; <3h; ≥3h
Variables calculated on a per-subject basis including data of all cycles	Number of cycles initiated	Number of cycles initiated per subject according to the following definition: A cycle will be qualified as “initiated” if at least 1 dose (non null) of study drug was administered in this cycle.
	Number of cycles completed	Number of cycles completed = number of cycles initiated, in case a subject drops out at the end of a cycle (i.e. at Day 22 or later, with last infusion at Day 22 administered in case of weekly treatment), but before start of next cycle. Number of cycles completed = number of cycles initiated – 1, in case a subject drops out within the last cycle.
	Number of cycles with all infusions completed	Number of cycles with all infusions completed (i.e. study drug administration page is filled for all intended infusions of the cycle and it is not ticked “Infusion not given”).)
	Number of infusions administered	Number of all infusions where a study drug administration page is filled and it is not ticked “Infusion not given”.
	Percentage of infusions administered	Number of infusions administered/ Number of planned infusions from Cycle 1, Day 1 up to and including the last visit for which the question “Was treatment modified” was answered (in any form).
	Number of infusions administered with any modification	Number of all infusions with any treatment modification except “Infusion not given”.
	Average percentage of actual volume administered vs. planned volume [%]	Mean of the variable “Percentage of actual volume administered vs. planned volume [%]” over all infusions
	Total actual dose	Sum of the variable “Actual dose

	administered [mg/kg]	administered [mg/kg]" over all infusions
	Total actual dose administered [mg]	Sum of the variable "Actual dose administered [mg]" over all infusions
	Average actual dose administered [mg/kg]	Mean of the variable "Actual dose administered [mg/kg]" over all infusions
	Number of infusions not given	Number of all infusions with "Actual volume administered [mL]" of zero. Missing data will be replaced as described above.
	Percentage of infusions not given [%]	Number of infusions not given / Number of planned infusions from Cycle 1, Day 1 up to and including the last visit for which the question "Was treatment modified" was answered (in any form)

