	Percentage of actual dose vs. planned dose [%]	Total actual dose taken [mg]/ Planned dose [mg] Where planned dose = sum of (starting dose of each cycle * 21 days), calculated over all cycles initiated. Starting dose of each cycle is taken from eCRF POM administration page for Day 1 of each cycle
	Number of days with missed doses	Sum of durations of intake of zero dose [=Start date – Stop date + 1] over all entries (in the eCRF POM administration log) with reason other than “Subject is in Rest Period between Day22 and Day28”
	Any dose reduction	Any reduced dose (compared to starting dose in first cycle)
	Any permanent	Discontinuation of POM but continuation of

	discontinuation of POM but continuation of MOR03087	MOR03087 during at least 2 MOR03087 infusions until last MOR03087 dosing day
Exposure to Dexamethasone		
Variables calculated on a per-subject basis including data of all cycles	Number of applications	Number of DEX intakes where a study drug administration page is filled and the question “Was dexamethasone taken?” is answered with “Yes”.
	Total actual dose taken [mg]	Sum over all doses administered
	Average actual dose taken during days treated [mg]	Total actual dose taken [mg]/ number of intakes
	Number of infusion days without administration of DEX	Number of all MOR03087 infusions where a study drug administration page is filled out and it is not ticked “Infusion not given” but DEX is not taken
	Any dose reduction	Any reduced dose (compared to starting dose in first cycle)
	Any permanent discontinuation of DEX but continuation of MOR03087	Discontinuation of DEX but continuation of MOR03087 during at least 2 MOR03087 infusions until last MOR03087 dosing day

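### SAP Table 5 writes the LEN and POM intake duration with its dates reversed, and its percentage-of-planned-dose row measures delivery against each cycle's own starting dose, not the assigned dose

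*SAP*

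**What the plan says.** All of this is in SAP Section 7.3.6, Table 5, in the lenalidomide and pomalidomide blocks.

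- *Number of days treated*, for both drugs: "Sum of durations of intake [=Start date – Stop date + 1] over all entries" with a non-zero dose. *Number of days with missed doses* uses the same date order; the POM row reads "Sum of durations of intake of zero dose [=Start date – Stop date + 1] over all entries". That makes four formulas.
- *Total actual dose taken*: "Sum of (durations of intake * dose [mg]) over all entries (in the eCRF LEN administration log"), and the same for POM.
- *Percentage of actual dose vs. planned dose*: total actual dose over planned dose. "Where planned dose = sum of (starting dose of each cycle * 21 days), calculated over all cycles initiated". For LEN, "Starting dose of each cycle is taken from eCRF LEN administration page for Day 1 of each cycle"; for POM, "Starting dose of each cycle is taken from eCRF POM administration page for Day 1 of each cycle".
- *Average daily dose taken during study*: "Total actual dose taken [mg]/ Duration of treatment [weeks] *7".
- A cycle counts as initiated "if at least 1 dose (non null) of study drug was administered in this cycle". This definition stands only in the MOR03087 block.

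Elsewhere in the same table the date order is the usual one. Duration of treatment is last dosing day minus first plus 1, and infusion duration is stop time minus start time. *Any dose reduction* is judged against the starting dose of the first cycle. SAP Section 10.7 summarizes all per-subject exposure variables, so these rows will be reported for Parts D and E.

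**The concern.** There are two separate problems.

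First, the duration formula is wrong as written. It is correct only for one-day entries and gives zero or negative days for anything longer. Total dose is built on it, and the percentage is built on total dose.

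Second, the denominator resets at every Day 1. Protocol Section 9.1.4 allows LEN and POM reductions throughout the study, in steps of 25/15/10/5 mg and 4/3/2/1 mg. A reduced dose in force on Day 1 lowers actual and planned dose together, so the row can read 100% for a subject well below the assigned dose. A reader who sees a percentage of planned dose in a combination study may take it as the share of the assigned LEN or POM delivered. The row does not measure that.

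**Working it through.** The SAP states no numerical value for this row, so there is no figure to reproduce. The formulas can be evaluated directly. Assigned doses (LEN 25 mg, POM 4 mg, Days 1-21) are from Protocol Section 7.1 and the reduction steps from Protocol Tables 4 and 6. The dosing histories are illustrative assumptions.

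**Date order**

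- As written, a Day 1-21 entry gives 1 - 21 + 1 = -19 days. Stop minus start plus 1 gives 21 - 1 + 1 = 21.
- As written, a two-day entry gives 0 days and a one-day entry gives 1.
- One full LEN cycle at 25 mg: -19 × 25 = -475 mg as written; 21 × 25 = 525 mg corrected.
- Six full cycles at 25 mg: -475 × 6 = -2850 mg as written, and -2850/3150 = -90.5%. Corrected, 3150/3150 = 100%.

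**Reduced dose in force on Day 1** (corrected dates; LEN 25 mg in Cycle 1, 15 mg in Cycles 2-6, all capsules taken, reduction effective at the start of Cycle 2)

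- Taken: 21 × (25 + 5 × 15) = 21 × 100 = 2100 mg.
- Planned under the SAP: the same sum, 2100 mg. Row: 2100/2100 = 100%.
- Assigned: 25 × 21 × 6 = 3150 mg. Share of assigned dose: 2100/3150 = 66.7%.

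**Day 1 dose recorded as 0, dosing resumed later in the cycle** (corrected dates; LEN 25 mg in Cycle 1; Cycle 2 with 7 days at 0 and 14 days at 15 mg)

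- Taken: 525 + 14 × 15 = 525 + 210 = 735 mg.
- Planned under the SAP: 525 + 0 × 21 = 525 mg. Row: 735/525 = 140%.
- Assigned: 2 × 525 = 1050 mg. Share of assigned dose: 735/1050 = 70%.

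**Hold and reduction inside a cycle that starts at full dose** (LEN 25 mg for 10 days, 4 days held, 15 mg for 7 days, one cycle)

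- Taken: 250 + 105 = 355 mg. Both denominators are 525 mg, so both percentages are 67.6%. The row does register a shortfall inside a cycle.

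**Missing bracket**

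- Read left to right, total/weeks × 7 exceeds total/(weeks × 7) by a factor of 7 × 7 = 49.

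**The case against.** The strongest reply is that the denominator is not an error. Table 5 defines it openly, and delivery against the dose prescribed for the cycle is a coherent measure. After a protocol-directed reduction, the lower dose can fairly be called the planned dose. The SAP nowhere calls the row relative dose intensity. This stands: the denominator is a matter of labelling and completeness, not a miscalculation.

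The second reply is that reductions are visible elsewhere: total dose, the two average daily doses, missed-dose days, the reduction flag and the permanent-discontinuation row. This also stands, although the rows built on intake duration depend on the date order being corrected.

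The third is that the dates and the bracket are typing slips. The same table shows the intended date order, negative days would probably be noticed in programming, and the mg/day label settles the bracket. That is likely, but four formulas in an analysis specification should not depend on it.

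Some stronger readings are tempting but not supported:

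- A reader might infer that Table 5 is inconsistent because MOR03087 exposure uses the assigned dose. Protocol Section 9.1.4 gives dose-reduction steps only for POM, LEN and DEX, so no such contrast arises.
- A reader might infer that the protocol always carries a reduced dose forward. No rule there says so explicitly, and Protocol Table 5 also allows LEN to restart at the same level after neutropenia under stated conditions.
- A reader might infer that cycles after permanent LEN or POM discontinuation make the present row ambiguous. With a Day 1 dose of 0 they add nothing to either sum, so counting them or not leaves the percentage unchanged.

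**Conclusion.** The point holds as a minor correction to the description of exposure. The date order is a wrong stated rule in four formulas and affects total dose and the percentage. The percentage row is usable only as delivery relative to the cycle's starting dose. It differs from the share of the assigned dose when a cycle starts at a reduced or zero dose: 100% against 66.7%, and 140% against 70%, in the cases worked above.

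The size in practice is unknown, because the documents give no expected frequency of reductions. The 140% case also assumes that a zero is entered for Day 1. Protocol Section 9.1.4 redefines Day 1 when a delayed cycle resumes, but it is unclear whether that applies while MOR03087 continues. The planned table descriptions in the SAP are blacked out, so a footnote may already state the denominator; this conclusion rests on the Table 5 text.

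A reader might infer that reported exposure will be negative or inflated 49-fold, or that reductions are hidden from the report. The documents do not support either: the intended formulas can be recognized from the same table, and other rows show reductions. No endpoint and no MTD or DLT decision uses the row.

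**What to change.** In SAP Table 5:

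1. Write duration of intake as stop date minus start date plus 1 in all four places (days treated and days with missed doses, LEN and POM).
2. Put duration of treatment in weeks times 7 in brackets in the average daily dose row, for both drugs.
3. Relabel the present percentage as relative to the cycle starting dose, and state how a recorded Day 1 dose of 0 is handled, consistently with Protocol Section 9.1.4.
4. Add a relative dose intensity row with denominator assigned Cycle 1 dose × 21 × cycles initiated. State in that row whether cycles after permanent LEN or POM discontinuation count. The choice matters for this new row: for LEN 25/15/15 mg then stopped, with MOR03087 continued to Cycle 6, 21 × 55 = 1155 mg is 1155/1575 = 73.3% up to the stop and 1155/3150 = 36.7% over all six cycles.

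The cost is SAP wording and minor programming, with no new data. The new percentage equals the present row when no cycle starts at a reduced or zero dose. Where they differ, a footnote should give both denominators.
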